2.6 Eltrombopag for Refractory Severe Aplastic Anemia

Reasoning that eltrombopag stimulated primitive HSCs and progenitors and as there was a clear deficit in HSC numbers and function in SAA, in 2009 we initiated a single-arm dose escalation phase 1/2 trial for patients with refractory SAA. For protocol entry, all patients had to have severe thrombocytopenia in addition to fulfilling criteria for SAA, and they must have failed at least one prior regimen of standard ATG-containing immunosuppressive therapy. The primary endpoints were safety and clinically significant hematologic response. The study design and response criteria are shown in Supplemental Figure 1.

At termination, 26 patients were enrolled in the protocol and 25 had received study drug. As shown in Table 1, this patient population had very prolonged and serious cytopenias. All were platelet transfusion-dependent, and most also required frequent red blood cell transfusions, and were severely neutropenic and thus susceptible to life-threatening infections. All had failed at least one prior cycle of high dose immunosuppression more than six months prior to study entry, with the majority failing two and some as many as four prior cycles of immunosuppression. The median time since last immunosuppression was 14 months, with a range of up to 117 months, excluding any chance that responses could be attributed to prior immunosuppressive therapy.

Table 1. Baseline Characteristics of Study Patients.

Number of patients	26
Age (median)	44
Range	18-77
Race	N (%)
White	12 (46)
African American	7 (27)
Asian	1 (4)
Hispanic	6 (23)
Male sex	14 (54)
Time from last IST (Mo.)	
Median	14
Range	6-117
Transfusion dependent	
PRBCs	23 (88)

Number of patients	26
Platelets	25 (100)
Baseline parameters	Median (range)
Platelets (K/ μ L)	9 (5-15)
Neutrophils (K/ μ L)	0.8 (0.07-2.8)
Hemoglobin (g/dL)	8.0 (6.0-13.8)

Hematologic	Gingival bleeding	1	100	Unlikely

Category	Event	N	Dose (mg)	Related to eltrombopag
Infection	C. difficile colitis	1	150	Unlikely
	Neutropenic fever	6	100, 150 x3, off x 2Off x 6	Unlikely
		1	150	Unlikely
	Gastroenteritis	1		Unlikely
Constitutional muscle weakness	-	1	-	Possibly
Dermatology/skin Rash	-	1	-	Possibly
Metabolic ALT, AST increased	-	1	-	Possibly
Psychiatric Depression	-	1	-	Possibly

AE, adverse event; ALT, alanine aminotransferase; AST, aspartate aminotransferase; SAE, severe adverse event.

Prior studies in patients with chronic ITP have raised the concern that TPO mimetics, including eltrombopag, might increase bone marrow reticulin deposition.⁵² We performed bone marrow biopsies with reticulin staining at baseline and after three months of eltrombopag treatment to assess for fibrosis. Patients on the extended access protocol underwent bone marrow biopsies with reticulin staining every six months. Reticulin deposition was graded by a single hematopathologist in a blinded manner on a scale of 0-4 according to standard guidelines. Two patients refused to have the 12-week response assessment bone marrow performed. Among 23 patients assessed, there was no significant increase in reticulin staining either at three months, or on serial biopsies in patients on prolonged eltrombopag treatment (Supplemental Fig. 4).

Eltrombopag has an FDA warning for cataract formation based on a prior study in ITP patients. We performed ophthalmologic examinations to assess for cataracts at baseline, after three months on eltrombopag, and every six months in patients on the extended access protocol. One patient was found to have a new lens opacification prompting discontinuation of eltrombopag, but this finding was not confirmed on a second examination performed 2 months later, or on subsequent serial eye examinations. No other patients had new cataract formation or worsening of existing cataracts after treatment with eltrombopag.

Marrow biopsies were performed at study entry, at the 12-week response assessment, and for responders at one year after study entry. Supplemental Figure 4 shows pre-treatment and one-year biopsies. There is striking normalization of cellularity in three of four responders. There was no increase in reticulin on 12-week biopsies in any patient, and no increase in fibrosis in follow-up marrows at 6 or 12 months in responders remaining on the extension phase.

Of the 14 non-responders, two patients died of disease progression, from complications of severe cytopenias. Two patients showed morphologic changes and cytogenetic abnormalities (monosomy 7) consistent with progression to myelodysplasia; one patient ultimately died, and the other underwent allogeneic stem cell transplantation. Progression to monosomy 7/MDS is concerning, given the controversy regarding whether chronic G-CSF increases progression to MDS in SAA as summarized above, and the warning regarding progression of MDS to AML for patients being treated with an alternative TPO-mimetic, romiplostim. Of note, romiplostim directly binds to the thrombopoietin receptor (c-mpl) and competes with endogenous thrombopoietin; while eltrombopag binds to a transmembrane domain of c-mpl leading to signal transduction. The distinct mechanism of action between the 2 thrombopoietin mimetics may account for differences in efficacy and safety profiles between them. In our cohort of over 400 patients with SAA followed long-term, approximately 15% progress to clonal disease including myelodysplasia and leukemia, and therefore two patients out of 25 enrolled is not unexpected. Our experience also suggests that patients with long-standing severe refractory disease and who lack of a robust response to initial immunosuppression, as were enrolled on our protocol, are the most likely to progress.

2.7 Rationale for Dose Selection

Eltrombopag 150 mg once daily has been selected as the starting dose for this study because this regimen has been safe and effective in increasing platelet counts in our recently-completed non-randomized, off label, pilot phase II study (NCT00922883) of eltrombopag as a single agent in patients with refractory SAA. 25 patients (age range 18-77 years) received 50mg daily of eltrombopag with dose escalation every two weeks to a maximum dose of 150mg daily. Patients were successfully escalated to the 150mg daily dose without observing any dose-limiting toxicities. Hematologic responses were only observed while receiving the 150mg daily dosing; it is possible that patients would have responded to lower doses of drug had the dose not been escalated every two weeks. Therefore, the duration of therapy in this setting has not been well defined.

There is preliminary safety data with doses up to 300 mg per day in a number of different patient populations. In healthy subjects, a clear dose and exposure response was seen for eltrombopag doses of 10 mg to 200 mg once daily for 5 days, with geometric mean AUC (0- τ) values of 302 μ g/mL for the 200 mg once daily regimen.⁵³ Eltrombopag was well tolerated in healthy subjects at all dose levels. In a recently completed open label study for patients with soft tissue sarcomas (NCT00358540), eltrombopag

doses of up to 150 mg have been given in conjunction with chemotherapy, without significant side effects. The most extensive data on dosing and long-term side effects has been obtained in patients with chronic ITP. An initial randomized phase 2 trial, followed by two randomized phase 3 trials all showed efficacy for eltrombopag compared to placebo for increasing the platelet count utilizing doses of up to 75 mg per day.⁴⁹⁻⁵¹ In ITP subjects, there was a dose response for eltrombopag 30 mg to 75 mg once daily, with geometric mean AUC_(0-t) values of 169 µg/mL for the 75 mg once daily regimen. There was no significant difference between the safety profile of ITP subjects receiving 30, 50 or 75 mg of eltrombopag.

A starting dose of 75 mg once daily in East Asian and South East Asian patients will be used. Modified dosing for subjects of East Asian and South East Asian heritage (self-reported) has been implemented for the following reasons. In healthy Japanese subjects, plasma eltrombopag AUC_(0-t) was approximately 80% higher when compared to non-Japanese healthy subjects who were predominantly Caucasian. Similarly, in patients with ITP, plasma eltrombopag exposure was approximately 70% higher in East Asian and South East Asian subjects as compared to non-East Asian subjects who were predominantly Caucasian as higher drug exposure in East Asian and South East Asian subjects has been observed.

For pediatric subjects, there is a predicted higher weight-adjusted drug clearance than older children and adults based upon studies of several drugs approved for use in children, such as anticonvulsants, proton pump inhibitors, theophylline, and HIV protease inhibitors, have routinely demonstrated that young children have higher weight-adjusted drug clearance than older children and adults [Lamictal Package Insert, 2007; Trileptal Package Insert, 2007; Keppra Package Insert, 2008; Prilosec Package Insert, 2008; Kaletra Package Insert, 2007; Viracept Package Insert, 2007; Grygiel, 1983]. In the ongoing open-label phase of PETIT, a phase II pediatric chronic ITP study, subjects between 1 and 5 years received 1.2 – 2.5 mg/kg eltrombopag once daily, while subjects between 6 and 17 years of age received an average daily dose of 58.5 mg daily (NCT00908037). The maximum dose used in the PETIT trial among all age groups is 75 mg daily dose. Cohort 3 (ages 1 to 5 years) was opened for patient recruitment on 01 June 2011 and the initial group of 5 subjects has been enrolled. Preliminary data have been evaluated for an initial group of 5 subjects aged 1 to <6 years enrolled in Cohort 3 of PETIT. These subjects initiated dosing with 0.7 mg/kg once daily and increased to at least 1.4 mg/kg once daily by the Week 12 visit. Preliminary PK data collected for 3 subjects (ages ranging from 2 to 5 years) receiving eltrombopag 1.1 to 1.2 mg/kg once daily at Week 6 suggest that this regimen delivers plasma eltrombopag exposure similar to a 37.5 to 50 mg once daily regimen in adults. No new pediatric specific safety signal has been identified thus far. The available platelet count, safety, and PK data available for subjects enrolled in the PETIT trial support a starting dose of 2.5 mg/kg once daily for non-Asian subjects aged 2-5 years.

Thrombocytosis is a theoretical risk of eltrombopag treatment when high dosages are administered. However, thrombocytosis has not been observed in the 25 patients with refractory SAA who were treated with 150 mg per day. It is possible although unlikely that patients with previously untreated SAA, who may have better residual hematopoietic stem cell function, could develop very high platelet counts on eltrombopag. Thrombocytosis has been observed in healthy volunteers as well as in subjects with ITP, and there was a suggestion of a higher risk of thrombosis in patients on eltrombopag compared to placebo in the phase 3 randomized trials for chronic ITP.⁵¹ However, patients with ITP, in contrast to patients with SAA, have hyper-reactive platelets and an increased endogenous risk of thrombosis. In an extensive analysis of ITP patients treated long-term with romiplostim, an alternative thrombopoietin mimetic, there was no evidence for increased thrombotic events in the romiplostim-treated patients compared to controls.⁵⁴ In a meta-analysis of randomized trials using either eltrombopag or romiplostim, there was a numerically but non-statistically significant trend to increase the occurrence of thromboembolisms compared to controls.⁵⁵ In the current trial, based on concern regarding thrombosis, dose reductions of eltrombopag will be made if the platelet count reaches 200,000 per µL or greater.

2.9 Scientific and Clinical Justification of the Protocol

The combination of ATG, which lyses lymphocytes, and CsA, which blocks T-cell function, is responsible for survival rates comparable to those observed with transplant recipients.^{27,56} Hematology Branch efforts for the past 10-15 years have been focused on developing immunosuppressive regimens in SAA that would circumvent the limitations presently observed with h-ATG/CsA. The failure of more intensive immunosuppressive regimens to improve outcomes suggests that even if immune attack on the bone marrow can be interrupted, deficits in the number or expansion ability of HSCs may limit hematopoiesis in these patients. Clinical and laboratory data suggest that greatly diminished stem cell numbers limit the effectiveness of immunosuppression and contribute to relapse and evolution.⁵⁷ It is reasonable therefore to conclude that the addition of a hematopoietic growth factor capable of expanding primitive HSCs and progenitors would be useful.

One such hematopoietic growth factor, TPO, is a potent endogenous cytokine and the principal regulator of platelet production, as summarized above. A 2nd generation TPO-agonist, the nonpeptide mimetic eltrombopag, is administered orally, well tolerated and does not induce auto-antibodies, in contrast to first-generation TPO-R agonists such as megakaryocyte growth and development factor (MDGF). Eltrombopag has been shown to increase platelets in healthy subjects, patients with chronic immune thrombocytopenic purpura (ITP), and more recently shown to increase blood counts in patients with hepatitis C associated thrombocytopenia^{58,59} and now in SAA as single agent, in our recently completed trial which has been presented in abstract form and now published (N Engl. J. Med. 2012;367:11-9).⁶⁰ These surprising results suggested that eltrombopag, like thrombopoietin itself, might act on the hematopoietic stem cell and offer real clinical benefit in SAA by increasing stem cell number.

Since outcome is strongly related to the presence of early recovery and to the quality of the blood cell count response at 3 months after receiving antithymocyte globulin, an agent like eltrombopag in enhancing the quality and speed of hematologic recovery could both shorten time at risk for infections, bleeding and transfusions as well as potentially reduce the rates of late events linked to a deficient stem cell compartment, and thus improve survival. In a cohort of 122 patients with SAA at our institution treated with H-ATG and

CsA, survival was associated with early attainment of hematologic recovery (86% vs. 40% at 5 years, P<.001), and degree of blood count recovery at 3 months (90% vs. 42% for patients with less robust recovery).²⁷ Therefore, the addition of eltrombopag to standard immunosuppressive therapy is likely to have an impact on survival if the quality of hematologic recovery can be improved during the first 3 - 6 months of treatment.

The objectives of this trial are therefore to assess the effectiveness of eltrombopag alongside standard immunosuppressive therapy with h-ATG/CsA for treatment naïve severe aplastic anemia and to define the additive toxicity of eltrombopag with h-ATG/CsA. A secondary objective for this study will be to describe the common aspects of health-related quality of life (HRQL) in the adult subjects pre- and post-study treatment which is recommended by the FDA⁶¹ and the IOM⁶² as indicators of treatment effects.

2.9.1 Justification for adding Cohort 2 (August 2013)

In this study, we are observing more rapid hematologic improvement than observed with immunosuppression alone. The overall response rate of 84% (11/13) at 6 months, with 100% of these responses observed by 3 months, is also higher than in historical data. As subjects currently receive eltrombopag for 6 months but blood counts have improved by 3 months, it is possible that administration of eltrombopag may only be necessary for the shorter duration, lowering risk, cost, and inconvenience. In particular, limiting exposure to eltrombopag may reduce the risk of cytogenetic evolution. Further, in the event of relapse, expected with discontinuation of treatment, we can now not distinguish whether cyclosporine or eltrombopag is responsible, as both are administered concurrently. Therefore, we propose to treat another cohort (cohort 2) of 31 subjects, with no change to this protocol other than a reduction in eltrombopag administration from 6 to 3 months. The study objectives, primary and secondary endpoints, statistics – sample size, stopping rules, eligibility, monitoring and ancillary studies will remain unchanged. Responses at 3 months can be assessed for the two cohorts, providing a confirmation cohort for our early results, whereas new information will be provided by comparison of long-term outcomes between the two cohorts. These data can be used to inform design of a future randomized, multicenter phase III trial. Note amendment 17 was submitted on October 23, 2014 to increase Cohort 2 sample size to 33 subjects in order to allow subjects to be enrolled and treated while amendment 16 to add Cohort 3 was being reviewed. Note, only 31 subjects were enrolled into Cohort 2 because the Cohort 3 amendment was approved prior to needing to enroll the 2 additional subjects into Cohort 2.

2.9.2 Justification for adding Cohort 3 (September 2014)

As of September 15, 2014, 57 subjects have been enrolled on the protocol (31/31 in cohort 1, and 26/31 in cohort 2) and the combination of cyclosporine and eltrombopag has been safe and well tolerated. Higher overall response rates with eltrombopag compared to immunosuppression alone are a consistent observation from both the first and second cohort. Most subjects respond within 2-3 weeks of the first dose of eltrombopag alleviating the transfusion burden sooner than our historical cohort. In cohort 2, where eltrombopag is discontinued at 3 months in all subjects, all subjects have either maintained or normalized their blood counts between 3 and 6 months. In cohort 1 and cohort 2 eltrombopag was implemented to begin on Day 14 to avoid any potential hepatotoxicity from the combination of cyclosporine and h-ATG. However, now that we have ample data indicating the combination of cyclosporine and eltrombopag is safe, the earlier initiation of eltrombopag on Day 1 in combination with hATG should be tested in a third cohort. Therefore, we propose to treat another cohort (cohort 3) of 31 subjects, where eltrombopag will be administered without delay, starting Day 1, with the intention of accelerating hematologic recovery. Eltrombopag will be discontinued at the 6-month landmark visit.

2.9.3 Justification for adding Extension Cohort

An Extension Cohort of 87 subjects was added to the protocol once enrollment was completed in cohort 3 in order to allow additional subjects to be enrolled and treated while a new SAA treatment naïve protocol is developed and approved, and to obtain more precise data on secondary endpoints, and more pharmacokinetic data with the treatment regimen. We anticipate enrollment will be completed before we have a new SAA treatment naïve protocol developed and approved.

2.9.4 Justification for adding Laboratory Exploratory Cohort

We currently have accrued 178/182 patients to our protocol, 12-H-0150. Among these patients, 86 compose an extension cohort; the primary aim of extension of the study was to obtain more precise data regarding important secondary endpoints and to collect more pharmacokinetic samples.

We now propose an extension to add 25 subjects to perform novel laboratory experiments using *fresh* bone marrow samples obtained at the time of diagnosis and prior to institution of definitive therapy. **These experiments will not be feasible in our upcoming treatment naïve SAA protocol because we plan to initiate treatment remotely, and thus will not be collecting baseline marrow/blood samples for research.**

T cell mediated immune destruction of hematopoietic stem and progenitor cells (HSPCs) is the pathophysiology of SAA, but precise mechanisms have not been characterized, nor have biomarkers been identified. We intend to elucidate the pathophysiology of SAA using advanced single-cell methodologies (scRNA-seq), a technique that allows high resolution whole transcriptome profiling of the individual cells, and time of flight cytometry (CyTOF), a novel deep-phenotyping technique using multiparameter mass cytometry. scRNA-seq will be used to study the transcriptome of HSPCs and enriched T cells, and T cell clonality in patients with newly diagnosed severe aplastic anemia (SAA). CyTOF will enable high resolution characterization of HSPCs, immune cells especially regulatory T cell subsets, and other marrow populations simultaneously based on a range of cell surface and intracellular markers, to explore the relationship of bone marrow microenvironment and hematopoiesis in patients with SAA. If a biomarker or genetic signature is identified from these experiments, further experiments could be performed on larger cohort of frozen samples using simpler methods, such as standard flow cytometry or multiplex polymerase chain reaction (PCR).

Our aims are to:

- (1) Identify characteristic cell population in treatment naïve SAA, provide a comprehensive view of active marrow process in SAA patients at both cellular and molecular levels
- (2) Infer potential autoantigens from the expanded clonal T cells, perform integrated analysis of receptors and ligands of T cells and HSPCs
- (3) Expand our understanding of the interaction between HSPCs and the microenvironment of the marrow of SAA patients by interrogating immune mechanisms in detail (cytotoxic T cells, T regs, MDSC, macrophages)
- (4) Characterize transcriptomes programs in HSPCs in treatment naïve SAA
- (5) Identify biomarkers for clinical response and long term outcomes, particularly clonal evolution
- (6) Explore mechanisms by which eltrombopag (EPAG) stimulates hematopoiesis and modulates the immune system

We plan to perform this experiment with *fresh* bone marrow samples from 25 subjects at baseline and at 6 months' time point. These patients will not be included in the analysis on secondary endpoints of the current extension cohort. Fresh samples will be used for flow cytometry, particularly mass spectrometry, due to the impact of cryopreservation on fragile cell types and certain proteins. A study with human tumor specimen found

[figure not shown]
significant reduction of expression levels of multiple markers upon cryopreservation [70]. Fresh samples are desirable in single cell experiments using CD34 cells from SAA patients due to low cell numbers, which are inevitably decreased with cryopreservation. Additionally, there are data suggesting that cryopreservation results in molecular alterations in some cells including DNA damage, gene expression, and epigenetic changes[72, 73].

3. STUDY DESIGN

[figure not shown]
This study is designed as a non-randomized, pilot phase I/II study in which 182 subjects with severe aplastic anemia who have not received prior definitive immunosuppressive therapy will be treated with a standard regimen of h-ATG/CsA, combined with eltrombopag as experimental therapy. The first 31 subjects will be enrolled to cohort 1. Then up to 33 subjects will be enrolled to cohort 2 while up to 31 subjects will be enrolled in cohort 3. Subjects enrolled to cohort 1 will receive eltrombopag for 6 months whereas subjects enrolled to cohort 2 will receive eltrombopag for 3 months. Subjects enrolled in cohort 3 will initiate h-ATG, CsA and eltrombopag on Day 1. The primary clinical endpoint of this study is the quality of hematologic response at 6 months. In cohorts 1 and 2 eltrombopag will be initiated on day 14 to avoid overlap with the known transient hepatotoxicities associated with ATG and cyclosporine. Cohort 3 will initiate h-ATG, CsA, and eltrombopag on Day 1 if there are no significant hepatotoxicities seen in cohorts 1 and 2. Patient-reported outcome questionnaires (Appendix E) will be collected initially when the subject enrolls on-study (pre-ATG/CSA), pre-eltrombopag, at 3 and 6 months, and annually for 5 years.

Up to an additional 87 subjects may be enrolled into the Extension Cohort in order to allow subjects to be enrolled and treated while a new SAA treatment naïve protocol is developed and approved. In addition, 25 subjects will be enrolled for Laboratory Exploratory Cohort. The treatment schedule for both the Extension & Laboratory cohorts will be the same as Cohort 3.

Protocol Design for Cohort 1

[figure not shown]

Protocol Design for Cohort 2 added August 2013

[figure not shown]

*Cohort 2 will continue CsA administration month 6 to month 24 at 2.0mg/kg per amendment number 15

Protocol Design for Cohort 3 added September 2014

Protocol Design for Extension Cohort and Laboratory Exploratory Cohort

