parameters to be 3, i.e. the parameters of the beta prior distribution are 0.60 and 2.40. Since we have seen in the past that the first few subjects to be accrued are possibly sicker than the rest of the subjects in the sample, we will start safety monitoring the study when 3 or more subjects have developed specified TRSAEs. The following tables summarize the threshold numbers for stopping the study:

Number of Tx naïve SAA subjects enrolled	Stop if the number of Tx naïve SAA subjects who develop any of the specified TRSAEs reaches:
≤ 6	3
≤ 9	4
≤ 13	5
≤ 17	6
≤ 21	7
≤ 25	8
≤ 29	9
≤ 31	10
≤ 37	11
≤ 41	12
≤ 45	13
≤ 49	14
≤ 54	15

For the stopping rule we generated a study with 25 independent Bernoulli trials, each had a probability p for having the above TRSAE and $q=1-p$ for not having such TRSAE and compared the TRSAE outcomes with the above stopping boundary to determine whether the study was stopped. We repeated the simulation 100,000 times and computed the proportion of stopped studies (i.e. “number of stopped studies”/100,000), which were stopped using the above stopping rule. The following table summarizes the proportions of stopped studies under a number of scenarios for p :

Probability of “Monitored” TRSAE= p	5%	10%	15%	20%	25%	40%
Proportion of stopped studies	0.27%	2.45%	9.19%	22.57%	41.44%	89.81%
Average number of Tx naïve SAA subjects	24.95	24.58	23.59	21.78	19.30	11.02
Average number of Tx naïve SAA with a specified TRSAE	1.25	2.47	3.53	4.35	4.83	4.41

These results suggest that the above stopping rules have a low probability of stopping a study when the proportion of the corresponding specified TRSAE is below the benchmark value of 20%, and the probability of stopping a study is high when the true proportion of the above specified TRSAE exceeds this benchmark value. Based on these results, we believe that our Bayesian stopping rules have satisfactory statistical properties.

Extension Cohort

Following Amendment FF, we updated the TRSAE stopping rule for this expanded cohort of N=87 patients (55 patients in the original cohort, 32 additional patients) the TRSAE stopping rule is updated using the

same Bayesian approach (Geller et al., 2004) with the same assumptions. Specifically, the assumptions are:

- a) The rate of developing one or more of the specified TRSAEs is 20% or less.

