- b) The stopping boundary is reached if the Bayesian posterior probability that the true probability of developing one or more of the specified TRSAEs exceeds this benchmark rate of 20% is at least 90%.
- c) The prior distribution is a beta distribution with the sum of the two beta parameters to be 3, i.e. the parameters of the beta prior distribution are 0.60 and 2.40.
- d) The safety monitoring starts when 3 or more subjects have developed the specified TRSAEs.

The following tables summarize the threshold numbers for stopping the study:

Number of Tx naïve SAA subjects enrolled	Stop if the number of Tx naïve SAA subjects who develop any of the specified TRSAEs reaches:
≤ 6	3
≤ 9	4
≤ 13	5
≤ 17	6
≤ 20	7
≤ 24	8
≤ 29	9
≤ 33	10
≤ 37	11
≤ 41	12
≤ 45	13
≤ 49	14
≤ 54	15
≤ 58	16
≤ 62	17
≤ 66	18
≤ 71	19
≤ 75	20
≤ 80	21
≤ 84	22
≤ 87	23

We performed a simulation study to verify the appropriateness of this stopping rule. In each simulation run, we generated a study with 87 independent Bernoulli trials, each had a probability p for having the above TRSAE and $q=1-p$ for not having such TRSAE and compared the TRSAE outcomes with the above stopping boundary to determine whether the study was stopped. We repeated the simulation 100,000 times and computed the proportion of stopped studies (i.e. “number of stopped studies”/100,000), which were stopped using the above stopping rule. The following table summarizes the proportions of stopped studies under several different scenarios for the true value of p :

Probability of “Monitored” TRSAE= p	5%	10%	15%	20%	25%	40%

Proportion of stopped studies	0.27%	2.38%	10.35%	32.83%	66.73%	99.90%
Average number of Tx naive SAA subjects	86.78	86.13	79.57	66.31	47.15	12.58
Average number of Tx naive SAA with a specified TRSAE	4.34	8.50	11.93	13.27	11.79	5.04

These results suggest that the above stopping rule has a low probability of stopping a study when the proportion of the corresponding specified TRSAE is below the benchmark value of 20%, and the probability of stopping a study is high when the true proportion of the above specified TRSAE exceeds this benchmark value. Based on these results, we believe that our Bayesian stopping rule has satisfactory statistical properties.

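### The 25 Laboratory Exploratory subjects receive the Cohort 3 regimen, but section 9.5 gives them no numeric TRSAE stopping boundary

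*Combined protocol and SAP*

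**What the plan says.** Section 3 (Study Design) adds the cohort: "25 subjects will be enrolled for Laboratory Exploratory Cohort". It then fixes the regimen: "The treatment schedule for both the Extension & Laboratory cohorts will be the same as Cohort 3". The title-page table lists the cohort on its own line, separate from the Extension Cohort of 87.

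Section 9.5 (Stopping Rules) has two TRSAE boundaries.

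- The first is headed for Cohorts 1, 2 and 3. Its table runs to 54 enrolled, and its operating characteristics were simulated at 25 subjects.
- The second is headed for the Extension Cohort. Following Amendment FF, "we updated the TRSAE stopping rule for this expanded cohort of N=87 patients". Its last row is 23 events at up to 87 enrolled.

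The two rules share their assumptions. The boundary is reached when the posterior probability that the true TRSAE rate "exceeds this benchmark rate of 20% is at least 90" per cent. For the prior, "the parameters of the beta prior distribution are 0.60 and 2.40". And "The safety monitoring starts when 3 or more subjects have developed the specified TRSAEs".

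Neither section 9.1 nor section 9.5 names the Laboratory Exploratory Cohort. Section 2.9.4 separates it from the Extension Cohort for efficacy: "These patients will not be included in the analysis on secondary endpoints of the current extension cohort".

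**The concern.** A formal boundary fixes in advance how many events are too many. Every earlier cohort on this protocol has one. The 25 laboratory subjects receive the same three drugs from Day 1, and their laboratory purpose does not reduce that exposure.

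The protocol's own practice suggests an oversight rather than a decision. Section 9.1 states expressly that the stopping rules carry over to Cohorts 2 and 3. When Amendment FF added 32 Extension subjects, largely to supply fresh research samples, the boundary was recalculated and re-simulated for 87. The laboratory cohort was also added for fresh samples, without a matching update. Other safety text does name it: dose delay and interruption (5.3), ALT rules (5.5.2), relapse (5.7) and adverse event recording (10.2.3).

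If the TRSAE rate in these 25 subjects were well above 20%, no pre-specified count would call for a halt.

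**Working it through.** **Inputs (section 9.5).** Prior Beta(0.60, 2.40), benchmark rate 20%, posterior cut 90%, monitoring from the third subject with a TRSAE. Cohort size 25 (section 3).

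**Formula.** With s subjects having a TRSAE among n enrolled, the posterior is Beta(0.6 + s, 2.4 + n − s). Stop if s ≥ 3 and P(p > 0.20 | s, n) ≥ 0.90. The stopping probability at a true rate p comes from an exact binomial recursion, checking the boundary after each subject.

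**Step 1: reproduce the plan's figures from its printed tables.**

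| True rate | 5% | 10% | 15% | 20% | 25% | 40% |
|---|---|---|---|---|---|---|
| Extension, N = 87, stated | 0.27% | 2.38% | 10.35% | 32.83% | 66.73% | 99.90% |
| Extension, N = 87, exact | 0.26% | 2.44% | 10.56% | 32.86% | 66.92% | 99.91% |
| Cohorts 1–3, n = 25, stated | 0.27% | 2.45% | 9.19% | 22.57% | 41.44% | 89.81% |
| Cohorts 1–3, n = 25, exact | 0.27% | 2.41% | 9.14% | 22.52% | 41.41% | 89.69% |

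The method matches the plan's to within about 0.2 percentage points.

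**Step 2: apply the same rule to a separate cohort of 25.** For each s, find the largest n at which the posterior probability is still at least 0.90. For example, 7 events in 20 gives 0.919 and 7 in 21 gives 0.8995, so the row for 7 ends at 20. Likewise 8 in 24 gives 0.917 and 8 in 25 gives 0.899, so the row for 8 ends at 24, and 9 in 25 gives 0.956.

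| Enrolled | ≤6 | ≤9 | ≤13 | ≤17 | ≤20 | ≤24 | 25 |
|---|---|---|---|---|---|---|---|
| Stop at | 3 | 4 | 5 | 6 | 7 | 8 | 9 |

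| True rate | 10% | 15% | 20% | 25% | 30% | 40% |
|---|---|---|---|---|---|---|
| P(stop), separate n = 25 | 2.4% | 8.7% | 21.1% | 38.8% | 58.3% | 87.5% |

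**Step 3: the alternative of continuing the Extension count to 87 + 25 = 112.** The strict rule continues 23 (≤88), 24 (≤93), 25 (≤97), 26 (≤102), 27 (≤106), 28 (≤110), 29 (≤112).

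| True rate | 20% | 25% | 30% |
|---|---|---|---|
| P(stop), strict rule to 87 | 32.7% | 66.8% | 90.9% |
| P(stop), strict rule to 112 | 34.8% | 72.4% | 94.7% |
| Gain from the last 25 subjects, in points | 2.1 | 5.6 | 3.8 |

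Most of the pooled stopping probability comes from the first 87 subjects, who already have a boundary.

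**Step 4: protection for the 25 subjects themselves.** The documents give no TRSAE count for the Extension Cohort, so its rate is an assumption, shown as a range. Suppose the first 87 finish without stopping and the laboratory cohort then runs at 40%.

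| Assumed rate in first 87 | 10% | 15% | 20% |
|---|---|---|---|
| P(pooled rule stops among subjects 88–112) | 0.6% | 8.6% | 30% |

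The separate boundary stops with probability 87.5% at 40%, whatever happened earlier.

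**The case against.** The strongest reply is that these subjects are far from unmonitored, and that is correct. Section 10.2.3 names the cohort in its adverse event recording rules. Section 10.2.4 records serious events for as long as a subject is on study. Section 10.2.5.2 puts all events into DSMB reports, and sends unexpected, suspected serious events to the DSMB within 7 days (death or life-threatening) or 15 days (others). Section 10.1 lets the DSMB recommend termination. The ALT hold rules (5.5.2), the thrombosis rule (5.6.1) and the discontinuation criteria (9.6) also operate.

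A reader might therefore infer from the missing boundary that these events add nothing to the safety evidence, or that the trial cannot be stopped on their account. The documents support neither inference. What is missing is a numeric threshold.

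A second reply is that an existing rule already reaches the cohort. Section 2.9.4 calls the addition an extension, section 9.5 speaks of monitoring the study, and section 10.2.4 describes TRSAE monitoring without naming cohorts. This does not close the gap. Sections 1 (title-page table) and 3 list the cohort separately, the general wording in 9.5 sits under the heading for Cohorts 1, 2 and 3, and 10.2.4 refers back to 9.5. Even if the 25 are counted with the Extension Cohort, the printed table has no row beyond 87.

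A third reply is that pooling or separating is the sponsor's choice. That stands: the exclusion in 2.9.4 concerns secondary endpoints and settles nothing about safety counts. The case for a separate boundary rests on Step 4, not on the text.

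**Conclusion.** The point holds as a gap in the formal trigger. As written, section 9.5 assigns no TRSAE boundary to 25 subjects on the full Day-1 regimen, while every earlier cohort has one.

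The size of the gap is what the existing rule would have provided: a 58.3% chance of stopping at a true 30% rate and 87.5% at 40%. DSMB review mitigates this but has no stated threshold. The pooled probabilities of 72.4% at 25% and 94.7% at 30% should not be read as the benefit of covering these subjects, since 66.8% and 90.9% are already delivered by the first 87.

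The figures assume independent events with a constant rate within the cohort, a check after each subject, and the plan's own prior, benchmark and cut. The comparison with pooling also depends on the assumed Extension Cohort rate.

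**What to change.** State in section 9.5 that the Laboratory Exploratory Cohort is monitored for the same TRSAEs with its own 25-subject boundary under the existing prior, benchmark, posterior cut and start of monitoring. Print the seven rows and the operating characteristics from Step 2.

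The drafting cost is one sentence and two short tables. The statistical cost is a 21.1% chance of stopping this cohort when the true rate is the acceptable 20%. That is in line with the 22.57% the plan accepts where, for Cohorts 1 to 3, "we generated a study with 25 independent Bernoulli trials".

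If the sponsor prefers to pool, the Extension table can be continued to 112 with the rows in Step 3. This raises the stopping probability at 20% from 32.7% to 34.8%. Section 9.5 should then acknowledge that the pooled rule assumes a common event rate and reacts weakly if the first 87 subjects had few events.
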